#### 4.6.2.2. Pittsburgh Sleep Quality Index

The Pittsburgh Sleep Quality Index (PSQI) is a self-rated questionnaire which assesses sleep quality and disturbances over a 1-month time interval. Nineteen individual items generate seven "component" scores: subjective sleep quality, sleep latency, sleep duration, habitual sleep efficiency, sleep disturbances, use of sleeping medication, and daytime dysfunction, each scored 0 (no difficulty) to 3 (severe difficulty). The sum of scores for these seven components yields one global score (range 0 to 21). Higher scores indicate worse sleep quality.

#### Scoring:

##### PSQIDURAT

##### DURATION OF SLEEP

IF Q4  $\geq$  7, THEN set value to 0

IF Q4  $<$  7 and  $\geq$  6, THEN set value to 1

IF Q4  $<$  6 and  $\geq$  5, THEN set value to 2

IF Q4  $<$  5, THEN set value to 3

Minimum Score = 0 (better); Maximum Score = 3 (worse)

---

PSQIDISTB	SLEEP DISTURBANCE IF Q5b + Q5c + Q5d + Q5e + Q5f + Q5g + Q5h + Q5i + Q5j (IF Q5JCOM is null or Q5j is null, set the value of Q5j to 0) = 0, THEN set value to 0  IF Q5b + Q5c + Q5d + Q5e + Q5f + Q5g + Q5h + Q5i + Q5j (IF Q5JCOM is null or Q5j is null, set the value of Q5j to 0) $\geq 1$ and $\leq 9$ , THEN set value to 1  IF Q5b + Q5c + Q5d + Q5e + Q5f + Q5g + Q5h + Q5i + Q5j (IF Q5JCOM is null or Q5j is null, set the value of Q5j to 0) $> 9$ and $\leq 18$ , THEN set value to 2  IF Q5b + Q5c + Q5d + Q5e + Q5f + Q5g + Q5h + Q5i + Q5j (IF Q5JCOM is null or Q5j is null, set the value of Q5j to 0) $> 18$ , THEN set value to 3  Minimum Score = 0 (better); Maximum Score = 3 (worse)
PSQILATEN	SLEEP LATENCY First, recode Q2 into Q2new thusly: IF Q2 $\geq 0$ and $\leq 15$ , THEN set value of Q2new to 0 IF Q2 $> 15$ and $\leq 30$ , THEN set value of Q2new to 1 IF Q2 $> 30$ and $\leq 60$ , THEN set value of Q2new to 2 IF Q2 $> 60$ , THEN set value of Q2new to 3  Next IF Q5a + Q2new = 0, THEN set value to 0 IF Q5a + Q2new $\geq 1$ and $\leq 2$ , THEN set value to 1 IF Q5a + Q2new $\geq 3$ and $\leq 4$ , THEN set value to 2 IF Q5a + Q2new $\geq 5$ and $\leq 6$ , THEN set value to 3  Minimum Score = 0 (better); Maximum Score = 3 (worse)
PSQIDAYDYS	DAY DYSFUNCTION DUE TO SLEEPINESS IF Q8 + Q9 = 0, THEN set value to 0 IF Q8 + Q9 $\geq 1$ and $\leq 2$ , THEN set value to 1 IF Q8 + Q9 $\geq 3$ and $\leq 4$ , THEN set value to 2 IF Q8 + Q9 $\geq 5$ and $\leq 6$ , THEN set value to 3 Minimum Score = 0 (better); Maximum Score = 3 (worse)
PSQIHSE	SLEEP EFFICIENCY Diffsec = Difference in seconds between day and time of day Q1 and day Q3 Diffhour = Absolute value of diffsec / 3600 newtib = IF diffhour $> 24$ , then newtib = diffhour - 24 IF diffhour $\leq 24$ , THEN newtib = diffhour (NOTE, THE ABOVE JUST CALCULATES THE HOURS BETWEEN GNT (Q1) AND GMT (Q3)) tmpmse = (Q4 / newtib) * 100  IF tmpmse $\geq 85$ , THEN set value to 0 IF tmpmse $< 85$ and $\geq 75$ , THEN set value to 1 IF tmpmse $< 75$ and $\geq 65$ , THEN set value to 2 IF tmpmse $< 65$ , THEN set value to 3 Minimum Score = 0 (better); Maximum Score = 3 (worse)

PSQISLPQUAL	OVERALL SLEEP QUALITY Q6 Minimum Score = 0 (better); Maximum Score = 3 (worse)
PSQIMEDS	NEED MEDS TO SLEEP Q7 Minimum Score = 0 (better); Maximum Score = 3 (worse)
PSQI	TOTAL DURAT + DISTB + LATEN + DAYDYS + HSE + SLPQUAL + MEDS Minimum Score = 0 (better); Maximum Score = 21 (worse) Interpretation: TOTAL ≤ 5 associated with good sleep quality TOTAL > 5 associated with poor sleep quality

Analysis:

For the 7 "component" scores and the global score, absolute and changes from baseline will be summarised by treatment group and scheduled visit (as applicable). In addition, the same approach as for the primary endpoint (MMRM incorporating post-randomization data collected up to treatment discontinuation at week 12) will be used to provide estimates of the change from baseline to weeks 4 and 12.

4.6.2.3. Insomnia Severity Index

The Insomnia Severity Index (ISI) is a brief self-report questionnaire assessing the nature, severity, and impact of insomnia. The ISI comprises 7 items assessing the perceived severity of difficulties initiating sleep, staying asleep, and early morning awakenings, satisfaction with current sleep pattern, interference with daily functioning, noticeability of impairment attributed to the sleep problem, and degree of distress or concern caused by the sleep problem. Subjects rate each item on a scale of 0 to 4, yielding a total score ranging from 0 to 28.

Scoring:

The total score is calculated by adding the scores for all seven items. Higher scores indicate severe insomnia.

Analysis:

Absolute and changes from baseline will be summarised by treatment group and scheduled visit (as applicable) for the total score. In addition, the same approach as for the primary endpoint (MMRM incorporating post-randomization data collected up to treatment discontinuation at week 12) will be used to provide estimates of the change from baseline to weeks 4 and 12.

4.6.2.4. Hot Flash Related Daily Interference Scale (HFRDIS)

The HFRDIS is a 10-item, self-report questionnaire assessing the impact of hot flashes on a woman's life during the past week. For each of the 10 items, subjects rate how much hot flashes have interfered with that aspect of their life on a scale of 0 (not at all) to 10 (very much so).

Scoring:

The total score is calculated by adding the scores for all ten items. Higher scores indicate greater interference.

Analysis:

For each of the 10 items and the total score, absolute and changes from baseline will be summarised by treatment group and scheduled visit (as applicable). In addition, the same approach as for the primary endpoint (MMRM incorporating post-randomization data collected up to treatment discontinuation at week 12) will be used to provide estimates of the change from baseline to weeks 4 and 12.

4.6.2.5. MenQoL-I (1 month recall version)

The MenQoL-I (Menopause-specific Quality-of-Life Questionnaire Intervention Version) is a validated questionnaire used to measure condition-specific quality of life in menopausal women. It is composed of 32 items across 4 domains (physical, vasomotor, psychosocial and sexual). For each item, subjects record whether they have experienced the problem in the past month, and if so, they rate how bothered they were by the problem on a scale of 0 (not at all bothered) to 6 (extremely bothered). The item responses can then be converted into analysis scores and an overall questionnaire score.

Scoring:

The scale contains four domains:

- Vasomotor: items 1 to 3
- Psychosocial: items 4 to 10
- Physical: items 11 to 26, 30, 31, 32
- Sexual: items 27 to 29

Convert the item scores to a score ranging from 1 to 8 in the following manner:

Subject response	Analysis score
No	1
0	2
1	3
2	4
3	5
4	6
5	7
6	8

The score for each domain is calculated by the mean of the items contained in each (ranging from 1 to 8).

The overall questionnaire score is the mean of the domain scores.

Analysis:

For the 4 domain scores and the overall score, absolute and changes from baseline will be summarised by treatment group and scheduled visit (as applicable). In addition, the same approach as for the primary endpoint (MMRM incorporating post-randomization data collected up to treatment discontinuation at week 12) will be used to provide estimates of the change from baseline to weeks 4 and 12.

#### 4.6.2.6. Beck Depression Inventory II

The Beck Depression Inventory II (BDI-II) is a 21-item questionnaire assessing the intensity of depressive symptoms over the past 2 weeks. It is composed of items relating to symptoms of depression such as hopelessness and irritability, cognitions such as guilt or feelings of being punished, as well as physical symptoms such as fatigue, weight loss, and lack of interest in sex.

##### Scoring:

Subjects rate each item on a scale of 0 to 3, with the total score ranging from 0 to 63, with a higher score suggesting more severe depressive symptoms.

##### Analysis:

For the total score, absolute and changes from baseline will be summarised by treatment group and scheduled visit (as applicable). In addition, the same approach as for the primary endpoint (MMRM incorporating post-randomization data collected up to treatment discontinuation at week 12) will be used to provide estimates of the change from baseline to weeks 4 and 12.

#### 4.6.2.7. Handling of missing data on questionnaires

As MMRM is the main analysis, no handling of missing values will be done. Furthermore, at the time of the BDRM no excessive amount of missing data were observed on the questionnaires, so no imputation rules will be put in place.

#### 4.6.2.8. Subgroup analysis

The descriptive analyses of the co-primary endpoints analysis will be repeated by region (North America, Europe) on the FAS.

### 4.7. Pharmacokinetic Evaluations

Blood samples for assay of NT-814 plasma concentrations are collected at each of Weeks 2, 4, 8, and 12. The plasma NT-814 concentrations will be listed by scheduled visit on the Safety Population. Further details of the analysis of PK data will be described in an Exposure-Response Data Analysis Plan, and exposure-response data will be reported in a separate report.

### 4.8. Safety Analyses

Safety analyses will be conducted using the Safety Analysis Set.

#### 4.8.1. Treatment Exposure

Definitions of exposure variables for each drug are provided in Table 3.

**Table 3 Exposure variables definitions**

Variables	Definitions
Duration of dosing (days)	Last dose of randomised blinded treatment – first dose of randomised blinded treatment +1
Duration of dosing (weeks)	(Last dose of randomised blinded treatment – first dose of randomised blinded treatment +1) / 7

Study treatment compliance (%)	
<math>100 * (\text{total number of capsules taken}) / (\text{total number of capsules planned to be taken})</math>
 
Note: number of capsules planned to be received is 4*duration of dosing (in days).
 
Total number of capsules taken is calculated using the eCRF pages ‘Drug Accountability’ and ‘IMP dispense/administration’, based on the fact that each weekly card contains 32 capsules and four weekly cards will be dispensed at each of baseline, week 4 and week 8. Thus, one visit dispensed kit contains <math>32*4=128</math> capsules. At subsequent Visits (Weeks 4, 8 and 12) the number of capsules remaining within the 4 weekly cards is recorded and the number of capsules taken = <math>128 - \text{Number of capsules remaining in the 4 weekly cards}</math>.
 
In the event that the subject doesn’t return some or all of the 4 weekly cards at Week 4, 8 or 12, it will not be possible to determine the number of capsules taken, so protocol medication adherence taken will be set as missing. In the event that more than one kit was dispensed to the subject between 2 visits, in a same way it will not be possible to determine the number of capsules taken, so protocol medication adherence taken will be set as missing. Unscheduled visits will be also included in the calculation if Drug Accountability eCRF Form is completed.

Cumulative NT-814 exposure (mg)	
It is assumed that on a day the subject takes the 4 planned capsules:
 
In Placebo group, Cumulative dose = 0
 
In NT-814 40mg group, Cumulative dose = <math>(\text{number of capsules taken} / 4) * 40 \text{ mg}</math>.
 
In NT-814 80mg group, Cumulative dose = <math>(\text{number of capsules taken} / 4) * 80 \text{ mg}</math>.
 
In NT-814 120mg group, Cumulative dose = <math>(\text{number of capsules taken} / 4) * 120 \text{ mg}</math>.
 
In NT-814 160mg group, Cumulative dose = <math>(\text{number of capsules taken} / 4) * 160 \text{ mg}</math>.

The following information will be tabulated overall and by treatment:

- Summary of randomised drug exposure: Duration of dosing will be summarized quantitatively and qualitatively for the category ( $\leq 4$  weeks,  $>4-\leq 8$  weeks,  $>8-\leq 12$  weeks,  $>12$  weeks)
- Summary of cumulative NT-814 exposure (in mg)

- Summary of randomised study treatment compliance: Compliance will be summarized quantitatively and qualitatively for the category ( $\leq 50\%$ ,  $>50$  to  $\leq 80\%$ ,  $> 80\%$ ).

Listing of IMP dispense/administration and drug accountability data will be provided for the Safety Analysis Set. Placebo run in exposure data will be only provided in a listing for the Screen Analysis Set.

#### 4.8.2. Adverse Events

Adverse events will be coded using MedDRA Version 21.1 and displayed in tables and listings using SOC and PT.

Analyses of adverse events will be performed for those events that are considered treatment emergent (TEAE), where treatment emergent is defined as any adverse event with the onset date is on or after the date and time of first dosing with randomised study treatment. Any adverse event with an onset date earlier than the first dosing with randomised study treatment will be considered as a pre-treatment adverse event. In case there is any missing or incomplete onset date, the adverse event will be classified as treatment-emergent if the partial adverse event onset date/time information does not indicate that the adverse event started prior to the date and time of first dosing with study treatment. No imputation of adverse event dates/times will be performed.

If a subject experiences more than one AE with the same preferred term, that preferred term will be counted only once within summaries. It will be assigned the highest observed severity and the strongest relationship to study treatment among those events for the tables in which those characteristics are summarised.

An overview of adverse events will be presented and will include the number and percentage of patients with at least one:

- Treatment emergent adverse events
- Treatment emergent adverse events related to IMP
- Serious treatment emergent adverse events
- Treatment emergent adverse events leading to treatment discontinuation
- Treatment emergent adverse events leading to study discontinuation
- Treatment emergent adverse events leading to Death
- Severe treatment emergent adverse events

The number and percentage of subjects with the following adverse events will be presented by SOC and PT:

- Treatment emergent adverse event
- Serious treatment emergent adverse event
- Treatment emergent adverse event related to IMP
- Treatment emergent adverse event leading to treatment discontinuation
- Treatment emergent adverse events leading to study discontinuation

In addition, the treatment emergent adverse events will be summarized by SOC, by PT and by severity and by relationship to study treatment. For a patient with more than one occurrence of the same adverse event in a particular SOC/PT, only the adverse event with the most severe intensity and / or most extreme relationship to the study drug will be considered.

By-subject supportive listings will also be provided for the following:

- Pre-treatment AE;
- Treatment emergent adverse events;
- All Serious adverse events;
- Severe treatment emergent adverse events;
- Treatment emergent adverse events leading to treatment discontinuation;
- Treatment emergent adverse events leading to study discontinuation;
- Treatment emergent adverse events leading to death.

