#### **10.3.2 Physical examinations**

A full physical examination will be conducted at Screening Visit 2 and a symptom directed physical examination at the Baseline and Week 16 visits. This will be completed by a physician or an appropriately qualified delegate.

A full physical examination includes a review of the following body systems:

- General appearance
- Skin
- Head, eyes, ears, nose and throat
- Respiratory
- Cardiovascular
- Abdomen (including liver and kidneys)
- Musculoskeletal
- Neurological

Any abnormalities that are identified at Screening Visit 2 will be documented on the medical history eCRF page. Any change (including new and worsening findings) between Screening Visit 2 and the final study visit should be recorded as an AE on the AE eCRF page and in the subject's medical record.

If an improvement/resolution of a physical examination finding documented in the subject's medical history occurs during the study, it should be recorded in the source document. If there is resolution of a physical examination finding previously noted as an AE, then the event resolution and stop date should be recorded on the AE eCRF page and documented in the subject's notes.

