#### **10.5.4 Adverse Event Reporting**

Adverse events may be volunteered spontaneously by the subject, or discovered as a result of general, non-leading questioning. As the full medical history and physical evaluation does not take place until Screening Visit 2, the adverse event reporting period starts after this visit is

complete. Adverse events occurring from the time of Screening Visit 2 up to the final study visit will be recorded. All AEs should be recorded in the eCRF and in the subjects' source notes.

Any SAE occurring from Screening Visit 2 until 28 days after the last dose of IMP must be reported immediately (within 24 hours of the investigator becoming aware of it) and recorded on the SAE Form. Detailed instructions for the reporting of SAEs can be found in the Study Manual. All subjects with a SAE must be followed up and the outcomes reported. The investigator must supply the Sponsor and the relevant agency/IRB/IEC with any additional requested information (e.g., autopsy reports and terminal medical reports). Any follow-up information on a previously reported SAE will also be reported within 24 hours of awareness.

If the Investigator does not have all information regarding an SAE, he/ she will not wait to receive additional information before reporting the event and completing the appropriate data collection form. The Investigator should always provide a preliminary assessment of causality at the time of the initial report as described in Section 10.5.3.

The primary mechanism for reporting SAEs will be a paper collection form.

Scan & email of the SAE form is the preferred method to transmit this information to the project contact for SAE receipt although fax transmission is also acceptable. In rare circumstances and in the absence of email facilities or fax equipment, notification by telephone is acceptable, with a copy of the SAE data collection form sent by overnight mail. Initial notification via the telephone does not replace the need for the Investigator to complete and sign the SAE data collection form within the designated reporting periods.

If required according to local regulatory authorities and IRB/IEC policy, each Investigator must then notify his or her relevant agency/IRB/IEC of the SAE.

NeRRe is required to expedite to worldwide regulatory authorities reports of SUSARs in line with the relevant legislation. Fatal or life-threatening SUSARs must be reported within 7 calendar days and other SUSARs within 15 calendar days.

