### 11.10.1 Adverse Events

All adverse events will be coded using the current version of the Medical Dictionary for Regulatory Activities (MedDRA). Treatment-emergent adverse events (TEAE) will be presented within summary presentations, by MedDRA system organ class (SOC), preferred term and treatment group.

An adverse event will be defined as treatment emergent if the onset date is on or after the date of first dosing with study treatment. Any adverse event with an onset date earlier than the first dosing with study treatment will be considered as a pre-treatment adverse event. If a subject experiences more than one AE with the same preferred term, that preferred term will be counted only once within summaries. It will be assigned the highest observed severity and the strongest relationship to study treatment among those events for the tables in which those characteristics are summarised. Pre-treatment AEs will be identified in a subject listing.

Summary presentations for the number and percentage of subjects reporting TEAEs, severity of TEAEs, TEAEs by relationship to study treatment, and treatment emergent serious adverse events (SAE) will be presented by treatment group and overall. In addition, SAEs and adverse events directly resulting in withdrawal from study will be listed.

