#### 4.3.3. Safety analysis

An overview of adverse events will be presented and will include the number and percentage of patients in the different categories indicated in section 4.8.2.

The following information will be listed by treatment group for review at each meeting:

- Serious adverse events
- Withdrawals due to adverse events
- Other early study withdrawals with reason
- Severe adverse events
- Adverse events

Adverse event summaries will include all available data and will not be limited just to data through Week-4.

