Table 14.2.14.1	Mean Daily Frequency of Moderate and Severe Hot Flushes and Change From Baseline by Week and by Region (Full Analysis Set)
Table 14.2.14.2	Mean Weekly Severity of Moderate and Severe Hot Flushes and Change From Baseline by Week and by Region (Full Analysis Set)

*Displays of Adverse Events (CSR Section 14.3.1)*

Table 14.3.1.1	Overview of Treatment-Emergent Adverse Events (TEAE) (Safety Analysis Set)
Table 14.3.1.2	Treatment-Emergent Adverse Events (TEAE) by System Organ Class and Preferred Term (Safety Analysis Set)
Table 14.3.1.3	Serious Treatment-Emergent Adverse Events (TEAE) by System Organ Class and Preferred Term (Safety Analysis Set)
Table 14.3.1.4	Drug-Related Treatment-Emergent Adverse Events (TEAE) by System Organ Class and Preferred Term (Safety Analysis Set)
Table 14.3.1.5	Treatment-Emergent Adverse Events (TEAE) Leading to Treatment Discontinuation by System Organ Class and Preferred Term (Safety Analysis Set)

Table 14.3.1.6	Treatment-Emergent Adverse Events (TEAE) Leading to Study Discontinuation by System Organ Class and Preferred Term (Safety Analysis Set)
Table 14.3.1.7	Treatment-Emergent Adverse Events (TEAE) by System Organ Class, by Preferred Term and by Severity (Safety Analysis Set)
Table 14.3.1.8	Treatment-Emergent Adverse Events (TEAE) by System Organ Class, by Preferred Term and by Relationship to Study Treatment (Safety Analysis Set)

*Other Safety Information (CSR Section 14.4)*

Table 14.4.1.1	Clinical Laboratories: Hematology Actual Values and Changes Over Time on Study (Safety Analysis Set)
Table 14.4.1.2	Clinical Laboratories: Biochemistry Actual Values and Changes Over Time on Study (Safety Analysis Set)
Table 14.4.1.3	Clinical Laboratories: Bone Turnover Markers Actual Values and Changes Over Time on Study (Safety Analysis Set)
Table 14.4.1.4	Clinical Laboratories: Urinalysis Actual Values and Changes Over Time on Study (Safety Analysis Set)
Table 14.4.1.5	Clinical Laboratories: Urinalysis Categorical Actual Values Over Time on Study (Safety Analysis Set)
Table 14.4.2.1	Clinical Laboratories: Shifts from Baseline Versus Each Post-Baseline Visit for Hematology (Safety Analysis Set)
Table 14.4.2.2	Clinical Laboratories: Shifts from Baseline Versus Each Post-Baseline Visit for Biochemistry (Safety Analysis Set)
Table 14.4.3	Vital Signs: Actual Values and Changes Over Time on Study (Safety Analysis Set)

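### The SAP's onset-only treatment-emergent rule leaves placebo run-in AEs that worsen, become serious or lead to discontinuation on randomised drug out of every by-dose AE count

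*SAP*

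**What the plan says.** SAP 4.8.2 states that "treatment emergent is defined as any adverse event with the onset date is on or after the date and time of first dosing" with randomised treatment, and then gives the converse: "Any adverse event with an onset date earlier than the first dosing with randomised study treatment will be considered as a pre-treatment adverse event". Neither sentence refers to what happens to the event later. Protocol 11.10.1 has the same structure but a looser anchor: "Any adverse event with an onset date earlier than the first dosing with study treatment will be considered as a pre-treatment adverse event".

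AE collection starts well before the first randomised dose. Under protocol 10.5.4, "Adverse events occurring from the time of Screening Visit 2 up to the final study visit will be recorded". The two-week placebo run-in lies between Screening Visit 2 and Day 1.

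The only recording instruction that mentions worsening is in protocol 10.3.2, on physical examinations: "Any change (including new and worsening findings) between Screening Visit 2 and the final study visit should be recorded as an AE". The general AE rules in protocol 10.5.1 and 10.5.4 do not say whether a worsened AE receives a new record or a new start date.

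For the interim reviews, SAP 4.3.3 says: "An overview of adverse events will be presented and will include the number and percentage of patients in the different categories indicated in section 4.8.2". Every category in the 4.8.2 overview is treatment-emergent.

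**The concern.** A treatment-emergent definition normally covers two things: events that start on treatment, and events present beforehand that get worse on treatment. This plan has only the first. The gap matters here because the design creates a recorded two-week window on placebo just before randomisation, so AEs can be ongoing at Day 1.

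Worsening of an existing symptom after active drug starts is a possible drug effect. Safety and tolerability by dose is one of the two primary objectives (protocol 6.1), and protocol 11.1.2 says the DRC will use between-group differences in AE rates when it considers enlarging dose groups. At stake is whether the by-dose counts of severe, serious and discontinuation AEs are complete.

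**Working it through.** No arithmetic applies, because the point concerns a classification rule. I traced one case through the planned outputs: an AE that starts in the run-in, is held as a single record with its run-in onset date, and changes after the first randomised dose.

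1. **Classification.** Its onset precedes the first randomised dose, so SAP 4.8.2 makes it pre-treatment whatever follows. The SAP uses date and time of dosing, but this affects only the Day 1 boundary.
2. **Tables.** SAP 4.8.2 confines AE analyses to treatment-emergent events, and the eight AE tables in SAP 7.1 (14.3.1.1 to 14.3.1.8) are all titled accordingly. No table covers AEs with pre-treatment onset.
3. **Listings.** Of the seven by-subject listings in SAP 4.8.2, those for severe events, treatment discontinuation, study discontinuation and death are limited to treatment-emergent events. The SAE listing is not, and there is a separate pre-treatment listing.
4. **Interim outputs.** The overview counts inherit the treatment-emergent categories. SAP 4.3.3 then describes by-arm listings of SAEs, AE withdrawals, other early withdrawals, severe AEs and AEs, with no such limit.

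| Course after first randomised dose | Missing from | Still visible in |
|---|---|---|
| Severity increases | Tables 14.3.1.1, 14.3.1.2, 14.3.1.7; Listing 16.2.7.3 if severe | Pre-treatment Listing 16.2.7.7; interim listings of AEs and, if severe, severe AEs |
| Becomes serious | Tables 14.3.1.1, 14.3.1.3 | All-SAE Listing 16.2.7.2; Listing 16.2.7.7; interim SAE listing |
| Leads to stopping treatment or study | Tables 14.3.1.1, 14.3.1.5 or 14.3.1.6; Listings 16.2.7.4 or 16.2.7.5 | Listing 16.2.7.7; withdrawal reason in Table 14.1.1.2; interim listing of AE withdrawals |

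5. **Consistency between documents.** Protocol 8.5 and SAP 2.5.3 both name AE withdrawals as a safety endpoint with no treatment-emergent limit, although the protocol synopsis words its discontinuation endpoint in treatment-emergent terms. Protocol 11.10.1 says that SAEs and AEs directly causing withdrawal will be listed, again without a limit. The SAP lists only the treatment-emergent ones, while SAP section 5 reports no change from the protocol. Disposition Table 14.1.1.2 could therefore count an AE withdrawal that Tables 14.3.1.5 and 14.3.1.6 do not.
6. **Anchor.** Protocol 11.10.1 counts from the first dose of study treatment. Protocol 9.4, whose heading uses that same term, includes the run-in placebo and calls it IMP. Read literally, the protocol could make run-in AEs treatment-emergent already. The SAP says randomised study treatment in its main rule but drops the qualifier in its rule for incomplete onset dates.

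**The case against.** Four arguments on the other side have weight.

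- **The events are not lost, and the DRC can see them.** A reader might infer that such an event disappears from the safety record or is hidden from the DRC. The documents do not support that. The final pre-treatment and all-SAE listings keep it, and the interim listings as SAP 4.3.3 describes them would show it by arm. Only the counts, and the four limited final listings, omit it. This stands and narrows the point.
- **The exclusion depends on a recording convention.** If sites enter a worsening as a new AE with a post-dose start date, the present rule captures it. The annotated CRF that the SAP cites is not among the documents. This also stands: the omission is conditional on a single record being kept. Still, neither document requires a new record outside physical-examination findings.
- **The protocol may not share the defect.** If its study treatment includes run-in placebo, protocol 11.10.1 classes these events differently. That is a fair limit. It also means that the two documents need the same anchor.
- **The effect may be very small, and safety is only described.** A reader might infer a definite loss per arm, or that the active doses are made to look safer. Neither can be shown. One subject in an arm of 30 is 1/30 = 3.3 percentage points, against half-widths of 15 to 23 points at N=30 in protocol Table 11-1, but nothing in the documents says that even one such case per arm will occur. The rule applies to placebo as well as to every dose, so no direction of between-arm bias follows from the text. If the drug did worsen existing symptoms, the omissions would fall more on active arms, but that is a conditional statement.

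What remains is that a by-subject listing does not replace counts by dose.

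**Conclusion.** The point holds in a limited form. SAP 4.8.2, and protocol 11.10.1 if its study treatment means double-blind treatment, gives incomplete treatment-emergent counts for run-in AEs that change for the worse after randomisation. The omission covers all AE summary tables, the interim overview counts and the SAP's severe, discontinuation and death listings.

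This rests on one assumption, that the worsening stays in the original AE record. Its size cannot be estimated, because the documents give neither a run-in AE rate nor a rate of worsening. It is a gap in the completeness of safety reporting that is cheap to close. It is not evidence of a biased dose comparison.

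**What to change.** Change the SAP before unblinding:

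1. **Definition (SAP 4.8.2).** Extend treatment-emergent to any AE with onset before the first double-blind dose that, on or after that dose, increases in severity, becomes serious or leads to discontinuation of double-blind treatment.
2. **Identification.** Where the data do not date the worsening, settle the case by blinded review of AEs ongoing at Day 1.
3. **Discontinuations.** Tabulate and list all AEs leading to treatment or study discontinuation after randomisation, whatever their onset. This matches the AE-withdrawal endpoint in protocol 8.5 and SAP 2.5.3 and the listing in protocol 11.10.1.
4. **Anchor.** Use the first dose of double-blind (randomised) study drug throughout, including the SAP rule for incomplete onset dates, and record in SAP section 5 any resulting difference from the protocol.

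I would not add a new eCRF instruction or new text in protocol 10.5.4. The SAP already refers to the blinded data review as done (SAP 3.1 and 4.6.2.7), so such an instruction would come too late to be useful. A temporary interruption of dosing should not be a trigger by itself, because it would reclassify run-in events that had not changed.

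The cost is SAP wording, modest programming, a small blinded review and slightly higher treatment-emergent counts in all arms. Double counting does not arise, because SAP 4.8.2 already counts each preferred term once per subject.
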